9.2.1 Study time period

The overall study time period will span from 12 months (minimum look back period) prior to the country-specific anifrolumab market launch date until the latest available data at the last data extraction date. The **start of the study period** will be the market launch date of anifrolumab in each country (Table 4)

The **end of study period**, defined as the last possible day of follow-up when all patients still active are censored (30 September 2028 for Denmark, Finland, France and Germany; 30 September 2030 for USA). This will likely differ between countries as it is dependent on the length of data lag in each country at the time when the last data extraction is performed (Table 4). The rationale for this choice is to include all data available from relevant data sources to capture a sufficient number of outcomes, exposures, and linked mother-offspring pairs for the primary outcome at study, as reported in Section 9.4.

Table 4: Relevant dates of the study by country

Country	Start of study period Anifrolumab market launch date	Start of enrolment ¹ Date of first patient enrolled	End of enrolment ² Date of last patient enrolled	End of study period ³ Last possible day of follow-up, when all patients still active are censored
Denmark	11 March 2022	11 March 2022	29 September 2028	30 September 2028
Finland	Not launched	TBC	29 September 2028	30 September 2028
France	19 April 2022	19 April 2022	29 September 2028	30 September 2028
Germany	11 March 2022	11 March 2022	29 September 2028	30 September 2028

Country	Start of study period Anifrolumab market launch date	Start of enrolment ¹ Date of first patient enrolled	End of enrolment ² Date of last patient enrolled	End of study period ³ Last possible day of follow-up, when all patients still active are censored
USA	23 August 2021	23 August 2021	29 September 2030 ⁴	30 September 2030 ⁴

- 1 For *adverse birth outcomes* and *adverse outcomes related to infant growth* up to 1 year of age, due to the index date being birth/delivery, start of enrolment will begin 9 months after anifrolumab market launch date to allow for the observation of exposure during pregnancy.
- 2 For *CM outcomes* the last pregnancy will be included on 29 December 2026 (to allow for 9 months of pregnancy and 1 year after birth to be potentially observed).
For *adverse pregnancy outcomes* the last pregnancy will be included on 29 December 2027 (to allow for 9 months of pregnancy to be potentially observed).
For *adverse outcomes related to infant growth* up to 1 year of age the last offspring will be included on 29 September 2027 (to allow for 1 year after birth to be potentially observed).
For *adverse birth outcomes* the last offspring will be included on 29 September 2028 (no follow-up applicable).
- 3 Calculated assuming that the final report is due on 31 March 2032 and assuming a lag time of up to 2 years in data availability.
- 4 Due to shorter lag times in the USA data sources (see Section 9.4.1), an extra two years of data collection has been assumed

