Interim report 1 will contain descriptive analyses relevant to primary and secondary objectives, for data sources where relevant data is available for reporting. Descriptive analysis conducted in interim report 1 will be blinded to exposure. Interim report 2 will include all descriptive and comparative analyses using all available data at the time of reporting. Exploratory analyses, sensitivity analyses and meta-analyses will not be included in interim report 2.

The final study report is planned for 31 March 2032 and will include all descriptive, comparative, exploratory, sensitivity, and meta-analytic analyses for all data sources from all available data at that time.

- Protocol PRAC approval: Planned date 14 December 2023¹
- Registration EU PASS: Planned date 31 March 2024 (after PRAC endorsement of protocol and before data extraction)
- Progress report: Planned date 31 December 2024
- Anticipated date of first data extraction: Planned date 31 May 2025
- Interim report 1: Planned date 31 December 2027
- Interim report 2: Planned date 31 December 2030
- Last data extraction: Planned date 31 March 2031
- Final report of study results: Planned date 31 March 2032 (15 months after Interim report 2)

¹ This date is an assumption of PRAC approval of the protocol. All subsequent dates are dependent on the actual date of protocol approval by PRAC.

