Considering the estimated sample size required for this study, it is estimated that the selected data sources will provide a sufficient sample size to address the research questions (see Section 9.5). If it is determined at the time of interim reports, that the selected data sources will not provide the required sample size, mitigation approaches will be considered. These mitigation approaches include the use of additional data sources (which were deemed feasible but not currently selected), and extension of the study period.

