SNDS contains data on the presence and diagnosis date of long-term chronic disease (LTD). LTD is used together with PMSI to identify patients, namely those with SLE. Patients with LTD are eligible for 100% reimbursement of healthcare expenditure. The request for attribution of LTD is made by the general practitioner and it is not mandatory. Thus, it may be missing, for instance, if the medical expenses are already covered by another chronic disease or the treatment is not expensive. Diagnoses are coded using ICD-10.

SNDS also includes demographic data (including age, sex, place of residence, complementary universal health coverage status (as proxy to socio-economic status), date of death), health encounters, dispensations, medical devices, and laboratory tests (without results) (9). Information on occupational diseases and sick leaves are also available (104).

Data from DCIR and PMSI are annually updated and can be linked for each patient. At the time of the feasibility assessment, data were available until the end of 2021.

Study-specific data availability

The estimated annual number of pregnancies in women with SLE eligible for the MCM analysis and the select pregnancy loss outcomes analysis is 178 and 223, respectively (see Section 9.5.1 and Table 9).

Mother-offspring linkage is available since 2012, and all live births and stillbirths can be linked (10). This linkage is achieved using a deterministic approach.

In France, anifrolumab received marketing authorisation in February 2022 and entered the market in April 2022 (Table 4).

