9.9 Limitations of the research methods

Use of secondary data collected and maintained in electronic databases offers several scientific and operational advantages for conducting a pregnancy study, including specifically:

- The possibility of mitigating the information and selection bias that may affect primary data collection which involves a self-selected population of pregnant women and their infants.
- The opportunity to study all the eligible exposed and non-exposed pregnancies (i.e., no individual informed consent for this study is required) in women with SLE.
- The potential to optimise statistical efficiency with a 1:n (e.g., 1:3) match of exposed and non-exposed pregnancies.
- Additionally, national databases such as those from Nordic countries are known to be representative of the population of the country, typically containing lifetime data of patients and have demonstrably been used for research to obtain insights into the real-world use of pharmaceutical products. The presence of medical birth registries and registers of congenital malformation in some of these countries with high PPVs for adverse outcomes such as MCMs increases the internal validity of studies conducted using these national data sources.

The individual study databases have limitations typical of other real-world databases:

- Data are collected primarily for administrative purposes, so some medical information not directly related to reimbursement may be incomplete or not available at all. The accuracy of the available information may vary between data sources. This can affect the measurement of exposure to anifrolumab, the outcomes of interest and/or the covariates. To ensure that the accuracy of the retrieved information is acceptable, all data will be reviewed for possible inconsistencies or implausible information. Also, missing information may vary between data sources, and whenever applicable, missing information will be reported (please see Section 9.7).
- Information on all the study outcomes and individual covariates may not be available in all databases, in particular lifestyle variables and the up to 1-year assessment of growth of the infant.
- For some of the data sources, relatively long lag times must be considered, and these would vary by country. Thus, an assumption of a data lag time of approximately 2 years will be implemented.

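### Section 9.2.1 promises each source's latest data, yet Table 4 censors all four European countries 30 months before extraction; if that date binds, about 15 months of French data go unused

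*Protocol*

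**What the plan says.** **The rule.** Section 9.2.1 lets the overall period run to the most recent data on hand at the last extraction. Its stated reason is to use everything available, and it expects end dates to vary by country with the data lag. The Abstract says the same and fixes no European end date.

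**The dates.** The same section then sets "30 September 2028 for Denmark, Finland, France and Germany; 30 September 2030 for USA". Table 4 repeats this and defines it as the day on which everyone still active is censored. Footnote 3 explains: "Calculated assuming that the final report is due on 31 March 2032 and assuming a lag time of up to 2 years in data availability". Footnote 4 treats the USA differently because its lags are shorter: "an extra two years of data collection has been assumed". Footnote 2 gives last-inclusion dates, for example 29 December 2026 for congenital malformations.

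**The calendar.** The Abstract gives "Last data extraction: Planned date 31 March 2031", and the final report follows on 31 March 2032.

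**The lags.** Section 9.9 says "an assumption of a data lag time of approximately 2 years will be implemented". Table 8 lists 12 months for France, none for RHEKISS (Germany), 2-13 months for Denmark and 1-24 for Finland. Section 9.4.1.3 says the French data are updated annually and "At the time of the feasibility assessment, data were available until the end of 2021"; Section 9.4 dates that assessment to June 2022 to January 2023.

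**The use made of the date.** Section 9.5.1.2 carries September 2028 for every non-US source into the expected numbers exposed.

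**The concern.** The rule and the dates cannot both be followed. A programmer working from Table 4 and footnote 2 would censor French records at September 2028. One working from the text of Section 9.2.1 would keep everything in the extract.

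The stated lag does not account for the date either. Two years before extraction is 31 March 2029, and the largest European source has half that lag.

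France is where this matters. Table 12 assigns it 34% of the MCM sample, and it is the only European source expected in the MCM meta-analysis. MCM at 5% uptake with the 2032 report is also the only scenario in Table 13 with power below 80% (69% at 1:2, 72% at 1:3). Section 9.4 lists "extension of the study period" among the remedies for a shortfall, so data already expected in the extract should be used before the study is prolonged.

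**Working it through.** **1. Calendar.**
- 30 September 2028 to 31 March 2031: 30 months. The corresponding USA gap is 6 months.
- Extraction minus 2 years: 31 March 2029, which is 6 months later than Table 4.
- Footnote 3 counts from the report: 31 March 2032 minus 2 years is 31 March 2030, and a further 18 months back gives 30 September 2028. The milestones put only 12 months between extraction and report. The other 6 months are not explained.
- France, 12-month lag with annual releases: complete to 31 December 2029 at a March 2031 extraction, 15 months past the Table 4 date. With rolling releases it would be 31 March 2030, or 18 months. I use 15 as the cautious figure.

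**2. Reproducing the French counts.** Inputs from Sections 9.5.1.1 and 9.5.1.2: 558 SLE pregnancies a year, 50% moderate/severe, 80% without a confirmed teratogen, 80% exposed in the first trimester.
- Pregnancy loss: 558 × 0.5 × 0.8 = 223.2 a year.
- MCM: 223.2 × 0.8 = 178.6 a year.
- 19 April 2022 to 30 September 2028 is 6.45 years. At 10% uptake and 6.5 years: 223.2 × 0.10 × 6.5 = 145.1 and 178.6 × 0.10 × 6.5 = 116.1. Table 11 gives 145 and 116.

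The 2028 date therefore drives the 2032 rows.

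**3. Effect of 15 more French months (1.25 years).**

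| Uptake | Added, MCM | French MCM total | Added, pregnancy loss |
|---|---|---|---|
| 5% | 178.6 × 0.05 × 1.25 = 11.2 | 58 → 69 | 14.0 |
| 10% | 178.6 × 0.10 × 1.25 = 22.3 | 116 → 138 | 27.9 |

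**4. MCM power.** The method follows Section 9.5.1.3: binomial events per source at 7% in both groups, log RR with variance 1/a + 1/b (a, b = events in the exposed and comparator groups), fixed-effect inverse-variance pooling, and success when the upper 95% limit is below 2.5. I used 200,000 runs; a source with no event in one group contributes nothing to the pool.

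| Scenario | Exposed (Carelon / DAPI / France) | 1:2 | 1:3 | Table 13 |
|---|---|---|---|---|
| 5%, as planned | 51 / 56 / 58 | 66.2% | 72.9% | 69% / 72% |
| 5%, +15 months | 51 / 56 / 69 | 70.2% | 76.7% | not given |
| 10%, as planned | 102 / 114 / 116 | 96.0% | 98.2% | 96% / 98% |
| 10%, +15 months | 102 / 114 / 138 | 97.0% | 98.8% | not given |

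Three of the four stated values reproduce. The 69% differs by 2.8 points, which is compatible with the protocol's 1,000 runs (standard error about 1.5 points).

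**5. Against the requirement.** 51 + 56 + 69 = 176 exposed. Section 9.5.2 requires 210 (1:2) or 183 (1:3).

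**The case against.** **The text already states the rule.** Section 9.2.1, the Abstract and the description of the final report all point to using whatever data are available, and footnote 3 presents the dates as calculated under assumptions. On this reading Table 4 is only a planning table. This stands in part: a reader might infer that French data will certainly be discarded, and the documents do not establish that. But Table 4 defines the date as the censoring day, footnote 2 derives inclusion cut-offs from it, and Section 9.9 says the 2-year lag will be implemented. The flexible wording conflicts with these and does not override them.

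**Footnote 3 counts from the report, not the extraction.** True, and the USA date also sits 18 months before the report. Sections 6 and 11.1 mention data access of up to 18 months, but the protocol does not link that to this offset, and its own milestones leave 12.

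**The gain is small and planning on the early date is cautious.** True. Pregnancy-loss power exceeds 99% throughout, and assumptions will be reviewed at the interim reports.

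**The French gain may not materialise.** True. Section 9.4.1.3 says anifrolumab is visible in SNDS only while on the high-cost drug list, that the listing ended on 12 May 2022, and that France's suitability will be reassessed.

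**An early date is not needless everywhere.** True for Finland. Its malformation register lags three years, with plans for two (Section 9.4.1.2). Three years before extraction is 31 March 2028, earlier than Table 4.

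**Conclusion.** The point holds as an internal contradiction with a modest cost. A common European date of 30 September 2028 does not follow from the stated lag and extraction date, does not fit the French or German lags in Table 8, and conflicts with the section's own rule. If followed, it leaves about 15 French months unused: about 11 exposed MCM pregnancies at 5% uptake and 22 at 10%. The power gain is about 4 points at 5% uptake and 1 point (1:2) at 10%. These figures assume annual French releases with the Table 8 lag, the protocol's constant yearly numbers, and capture of anifrolumab in SNDS.

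Two stronger readings are not supported. A reader might infer that the extra French data would secure 80% power at 5% uptake and avoid the extension. They do not: power reaches 70% and 77%, whereas Table 13 reaches 80% and 84% only with the 2034 report. A reader might also infer that everything in Tables 10-13 rests on 2028. Tables 10, 11 and 13 also carry 2034 rows, and the required totals in Table 12 do not depend on the end date; only their split between sources does.

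**What to change.** - In Table 4, set each source's end date as last extraction minus that source's own lag for the outcome concerned: France about the end of 2029, RHEKISS close to extraction, and Denmark by its linked-register lag (3 to 15 months in Section 9.4.1.1). For Finland use the malformation-register lag of two to three years, which for MCM may give a date earlier than the present one.
- Make the last-inclusion dates in footnote 2 source-specific. For French malformation outcomes, 29 December 2026 would move about 15 months later, to about the end of March 2028.
- Reconcile footnote 3 and Section 9.9 with the 31 March 2031 extraction, and either explain or drop the 18-month offset.
- Recompute the 2032 and 2034 rows of Tables 10, 11 and 13 and the source split in Table 12, stating that the French figures depend on high-cost-list capture.

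The cost is minor table and analysis work, and end dates that differ between sources. No new data collection is needed, and the report date does not change.

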9.2.2 Participants

To address the research questions, eligible cohorts will be identified through a nested selection process (Figure 5). An *overall source population* will be created for data extraction (STEP 1) and split into *exposed to anifrolumab source population* and *unexposed to anifrolumab source population* (STEP2).

Then criteria common to exposed and unexposed to anifrolumab source populations will be applied to create post-data extraction *exposed to anifrolumab study population* and *unexposed to anifrolumab study population* (STEP 3) from where the cohorts of analyses will be derived (STEP 4).

Since this is a non-interventional observational study, minimal inclusion and exclusion criteria are desirable to minimise potential selection bias and represent real world clinical practice.

STEP 1

Inclusion criteria for data extraction to create an *overall source population*:

- Singleton³ pregnancies
- Women diagnosed with SLE

Exclusion criteria for data extraction to create an *overall source population*:

- Pregnancy associated with in vitro fertilisation (IVF)⁴

STEP 2

Step to create *exposed to anifrolumab source population* and *unexposed to anifrolumab source population*, from the overall source population (created in STEP 1).

STEP 2A - exposed to anifrolumab source population

Additional inclusion criteria to be applied after data extraction to create an *exposed source population*:

- Women with a continuous enrolment⁵ in the database for ≥ 12 months prior to LMP2
- Women diagnosed with SLE before pregnancy
- Women exposed to anifrolumab (polytherapy, added to SLE SOC) during pregnancy and/or 16-week period prior to LMP2⁶

Additional exclusion criterion to be applied after data extraction to create an *exposed source population*:

- Pregnancies whose date of conception cannot be established

³ Singleton pregnancies will be identified based on the coding system (e.g., ICD-10) used in the data sources (see [Table 18](#)). All pregnancies will be assumed to be singleton if there is no ICD-10 or procedural code that suggests the pregnancy is multifetal. For RHEKISS singleton pregnancy will be identified with the MedDRA code for single pregnancy. Multifetal pregnancies will be excluded because they share the same maternal exposure and it is not known how medication can be absorbed, distributed, and metabolised by each of the foetuses. Moreover, CMs as well as adverse pregnancy and birth outcomes occur more frequently in twin and triplet pregnancies than in singleton pregnancies, regardless of the exposure to the drug at study.

⁴ IVF pregnancies will be excluded due to issues related to the lack of information regarding maternal covariates in cases where a donor egg was used. Further, a higher incidence of adverse pregnancy and birth outcomes (e.g., gestational diabetes, gestational hypertension, preterm labour, low birthweight) have been reported in IVF pregnancies compared to spontaneously conceived controls ([118](#), [121](#)).

⁵ For example, a patient can be considered continuously enrolled in a specific time period if that patient had a contact with healthcare services (such as drug prescription or hospitalisation) prior to that period and if emigration or death were not notified after this contact. Criteria to define continuous enrolment in the database are country specific and will be detailed in the SAP.

⁶ The exposure period of interest for MCM outcomes is the first trimester of pregnancy and for all other outcomes, anytime during pregnancy. In order to account for potential prescriptions/dispensations/administrations that could lead to an intake during the period of interest, all prescriptions/dispensations/administrations that are recorded in the 16 weeks (time for anifrolumab concentration to fall below the LLOQ for 95% of patients) prior to LMP2 will be considered ([2](#)).

STEP 2B – unexposed to anifrolumab source population

Additional inclusion criteria to be applied after data extraction to create an *unexposed source population* (mirroring the exposed SLE source population, except for the exposure itself):

- Women with a continuous enrolment⁷ in the database for ≥ 12 months prior to LMP2
- Women diagnosed with SLE before pregnancy
- Women treated with SLE SOC during pregnancy⁸

Additional exclusion criteria to be applied after data extraction to create an *unexposed source population* (mirroring the exposed source population, except for the exposure itself):

- Women treated with anifrolumab during pregnancy and/or during the 16-week period prior to LMP2
- Pregnancies whose date of conception cannot be established

STEP 3

Step to create *exposed to anifrolumab study population* and *unexposed to anifrolumab study population*.

STEP 3A and 3B – exposed and unexposed to anifrolumab study population

Additional inclusion criteria to be applied to the exposed and unexposed source population for creating a post-data extraction overarching *exposed and unexposed study population* with only moderate to severe SLE (mirroring the exposed study population, except for the exposure itself):

- Women with moderate to severe SLE (severity assessment is based on the SLE severity algorithm, see Figure 7)

Additional exclusion criteria to be applied to the exposed and unexposed source population for creating a post-data extraction overarching *exposed and unexposed study population* (mirroring the exposed study population, except for the exposure itself):

- Women with mild SLE (severity assessment is based on the SLE severity algorithm, see Figure 7)

⁷ For example, a patient can be considered continuously enrolled in a specific time period if that patient had a contact with healthcare services (such as drug prescription/administration or hospitalisation) prior to that period and if emigration or death were not notified after this contact. Criteria to define continuous enrolment in the database are country specific and will be detailed in the SAP.

⁸ Exposure to SLE SOC will be assessed from LMP2 until end of first trimester for the outcome of MCM, and from LMP2 until end of pregnancy for all other outcomes. A look-back period of 5-half-lives of relevant drugs will be considered.

- Women with a history of CM or chromosomal abnormalities and genetic syndromes (according to available records)⁹, before delivery
- Women prescribed a confirmed teratogenic drug prior to LMP2 until end of first trimester (for MCM outcome) or end of pregnancy (all other pregnancy outcomes), with a look back period of 5-half-lives of relevant drug, in both the exposed and unexposed groups (see [Table 20](#))

To address the research questions related to the primary, secondary, and exploratory outcomes, cohorts and subgroups will be created. Additional selection criteria, to form the relevant population for each specific outcome, will be applied (*STEP 4*).

STEP 4 - Cohorts and sub-cohorts

For the purpose of the evaluation of MCM (primary outcome), the *MCM* cohort will be derived from the study populations ([Table 5](#)) and will include live and non-live offspring from mothers diagnosed with SLE (regardless of the exposure to anifrolumab, i.e., sub-cohorts *MCM_exp+MCM_unexp*).

For the purpose of the evaluation of mCM (secondary outcome), the *mCM* cohort will be derived from the study populations ([Table 5](#)) and will include live and non-live offspring from mothers diagnosed with SLE (regardless of the exposure to anifrolumab, i.e., sub-cohorts *mCM_exp+mCM_unexp*).

For the purpose of the evaluation of select pregnancy loss outcomes (composite of spontaneous abortion and stillbirth; primary outcome), and secondary outcomes (adverse pregnancy outcomes), the *pregnancy* cohort will be derived from the study populations ([Table 5](#)) and will include pregnant women diagnosed with SLE (regardless of the exposure to anifrolumab, i.e., sub-cohorts *pregnancy_exp+pregnancy_unexp*).

For the purpose of the evaluation of adverse birth outcomes (secondary outcomes), the *birth* cohort will be derived from the study populations ([Table 5](#)) and will include live offspring from mothers diagnosed with SLE (regardless of the exposure to anifrolumab, i.e., sub-cohorts *birth_exp+birth_unexp*).

For the purpose of the evaluation of adverse outcomes related to infant growth up to one year of age, the *infant* cohort will be derived from the study populations ([Table 5](#)) and will include live offspring from mothers diagnosed with SLE (regardless of the exposure to anifrolumab, i.e., sub-cohorts *infant_exp+infant_unexp*).

⁹ Several CMs in the mother are due to genetic syndromes/ microdeletions and chromosomal abnormalities which are heritable. These genetic syndromes/microdeletions are also causally associated with the outcomes of interest. The list of these syndromes/microdeletions and chromosomal abnormalities are provided in [Appendix D. Exemplar Codelists](#).

Additional inclusion and exclusion criteria to derive the abovementioned cohorts and sub-cohorts are listed in [Table 5](#).

Table 5: Cohorts and sub-cohorts as described in STEP 4, by objective

Objective	Main features	Input Cohort/ Population	Sub-cohort Abbreviation	Additional criteria to be applied to the input Cohort/ Population
Primary cohort MCM (MCM_exp+MCM_unexp)				

Primary objective 1 & 2;
 
Secondary objective 5a-b
 
Exploratory objective 15
	
Describe and estimate the risk and relative risk of MCM.
 
Describe cohort demographic and clinical characteristics.
 
Among live and non-live offspring
	Exposed study population	MCM_exp	
INCLUSION:
 
 • MCM: Pregnancies exposed to anifrolumab during the first trimester of pregnancy (+16 weeks prior to LMP2) • All pregnancies ending in spontaneous abortion, elective termination of pregnancy and stillbirth, regardless of linkage mother-offspring within the study period • Pregnancies with linkage mother-offspring within the study time period 
EXCLUSION:
 
 • Adopted children (where information is available)

Primary objective 1 & 2;
 
Secondary objective 5a-b
 
Exploratory objective 15
	
Describe and estimate risk and relative risk of MCM.
 
Describe cohort demographic and clinical characteristics.
 
Among live and non-live offspring
	Unexposed study population	MCM_unexp	
INCLUSION:
 
 • All pregnancies ending in spontaneous abortion, elective termination of pregnancy and stillbirth, regardless of linkage mother-offspring within the study period • Pregnancies with linkage mother-offspring within the study time period 
EXCLUSION:
 
 • Pregnancies exposed to anifrolumab during the first trimester (+16 weeks prior to LMP2) (see Section 9.3.1) • Adopted children (where available)

Objective	Main features	Input Cohort/ Population	Sub-cohort Abbreviation	Additional criteria to be applied to the input Cohort/ Population
Secondary cohort mCM (mCM_exp+mCM_unexp)				
Secondary objective 5c-d, 6 & 7;	Describe and estimate the risk and relative risk of mCM. Describe cohort demographic and clinical characteristics. Among live and non-live offspring	Exposed study population	mCM_exp	
INCLUSION:
 
 • mCM: Pregnancies exposed to anifrolumab anytime during pregnancy (+16 weeks prior to LMP2) • All pregnancies ending in spontaneous abortion, elective termination of pregnancy and stillbirth, regardless of linkage mother-offspring within the study period • Pregnancies with linkage mother-offspring within the study time period 
EXCLUSION:
 
 • Adopted children (where available)
Secondary objective 5c-d, 6 & 7	Describe and estimate risk of and relative risk of mCM. Describe cohort demographic and clinical characteristics. Among live and non-live offspring	Unexposed study population	mCM_unexp	
INCLUSION:
 
 • All pregnancies ending in spontaneous abortion, elective termination of pregnancy and stillbirth, regardless of linkage mother-offspring within the study period • Pregnancies with linkage mother-offspring within the study time period 
EXCLUSION:
 
 • Pregnancies exposed at any time to anifrolumab (+16 weeks prior to LMP2) (see Section 9.3.1) • Adopted children (where available)
Primary and Secondary cohort pregnancy (pregnancy_exp+ pregnancy_unexp)				
Primary objective 3 & 4	Describe and estimate risk of select pregnancy loss outcomes (composite of spontaneous abortion and stillbirth), adverse	Exposed study population	pregnancy_exp	
INCLUSION:
 
 • Pregnancies exposed at any time to anifrolumab (+16 weeks prior to LMP2)

Objective	Main features	Input Cohort/ Population	Sub-cohort Abbreviation	Additional criteria to be applied to the input Cohort/ Population

Secondary objective 5c-d, 8 & 9
 
Exploratory objective 13 & 14
	
pregnancy outcomes, separately and as a composite of foetal loss
 
Estimate relative risk of select pregnancy loss outcomes (composite of spontaneous abortion and stillbirth), adverse pregnancy outcomes, separately and as a composite of foetal loss.
 
Describe cohort demographic and clinical characteristics.
 
Among pregnant women
			
 Ectopic pregnancies (except for ectopic pregnancy outcome)

Primary objective 3 & 4
 
Secondary objective 5c-d, 8 & 9
 
Exploratory objective 13 & 14
	
Describe and estimate risk of select pregnancy loss outcomes (composite of spontaneous abortion and stillbirth), adverse pregnancy outcomes, separately and as a composite of foetal loss.
 
Estimate relative risk of select pregnancy loss outcomes (composite of spontaneous abortion and stillbirth), adverse pregnancy outcomes, separately and as a composite of foetal loss.
 
Describe cohort demographic and clinical characteristics.
 
Among pregnant women
	
Unexposed study population
	
pregnancy_unexp
	
EXCLUSION:
 
 Pregnancies exposed at any time to anifrolumab (+16 weeks prior to LMP2) (see Section 9.3.1) Ectopic pregnancies (except for ectopic pregnancy outcome)

Secondary cohort birth (birth_exp+ birth_unexp)
				

Secondary objective 5c-d, 10 & 11
	
Describe and estimate risk of adverse birth outcomes.
 
Estimate relative risk of adverse birth outcomes.
 
Describe cohort demographic and clinical characteristics.
 
Among live offspring
	
Exposed study population
	
birth_exp
	
INCLUSION:
 
 Pregnancies exposed at any time to anifrolumab (+16 weeks prior to LMP2) Pregnancies with linkage mother-offspring within the study time period

Objective	Main features	Input Cohort/ Population	Sub-cohort Abbreviation	Additional criteria to be applied to the input Cohort/ Population
Secondary objective 5c-d, 10 & 11	Describe and estimate risk of adverse pregnancy outcomes. Estimate relative risk of adverse pregnancy outcomes. Describe cohort demographic and clinical characteristics. Among live offspring	Unexposed study population	birth_unexp	INCLUSION: 
• Pregnancies with linkage mother-offspring within the study time period EXCLUSION: 
• Pregnancies exposed at any time to anifrolumab (+16 weeks prior to LMP2) (see Section 9.3.1)• Adopted children (where available)
Exploratory cohort infant (infant_exp+ infant_unexp)				
Secondary objective 5c-d; Exploratory 12	Describe and estimate the risk adverse outcomes related to infant growth. Describe cohort demographic and clinical characteristics. Among live offspring	Exposed study population	infant_expSLE	INCLUSION: 
• Live offspring• Pregnancies exposed at any time to anifrolumab (+16 weeks prior to LMP2)• Pregnancies with linkage mother-offspring within the study time period EXCLUSION: 
• Adopted children (where available)• Preterm offspring born <37 gestational weeks
Secondary objective 5c-d; Exploratory 12	Describe and estimate the risk adverse outcomes related to infant growth. Describe cohort demographic and clinical characteristics. Among live offspring	Unexposed study population	infant_unexpSLE	INCLUSION: 
• Live offspring• Pregnancies with linkage mother-offspring within the study time period EXCLUSION: 
• Pregnancies exposed at any time to anifrolumab (+16 weeks prior to LMP2) (see Section 9.3.1)• Adopted children (where available)• Preterm offspring born <37 gestational weeks

